6.3 Baseline Assessments

Baseline assessments will be the most recent assessment prior to the randomization.

6.4 Duration of diabetes

Duration of diabetes will be calculated as:

- Duration of diabetes = (Year of screening visit – Year of Diagnosis) +
(Month of screening visit – Month of Diagnosis) / 12

Note: If the month of diagnosis is unknown, impute “1 (January)” for the calculation. Duration of diabetes will be displayed to one decimal place.

6.5 Medical History and Prior and Concomitant Medications

Medical history will be coded using Medical Dictionary for Regulatory Activities (MedDRA) version 21.0. Prior and Concomitant medications will be coded using the World Health Organisation (WHO) DRUG dictionary version March 2018.

6.6 Extent of Exposure and Compliance to Study Treatment

Study drug exposure during double blind treatment period will be calculated as:

- Exposure duration = (Date of Visit 6 - Date of Randomization Visit)

Note: In case of early withdrawal, the date when unused study treatments are returned will be used to calculate the exposure duration.

Treatment compliance during the double blind treatment period will be calculated as:

- Overall Compliance = $100 \times (\text{Number of tablets dispensed} - \text{Number of tablets returned}) / \text{Exposure duration}$

Note: Overall compliance will be displayed to one decimal place.

6.7 Efficacy Variables

At each scheduled visit, blood sample will be collected from each subject to evaluate HbA1c, fasting plasma glucose (FPG), fasting insulin, C-peptide and glucagon. Blood sample will be analysed in designated central laboratory. Body weight (Kg) will be measured at each scheduled visit.

HOMA-IR and HOMA- β will be evaluated by FPG and fasting insulin as follows:

- HOMA-IR = Fasting insulin (μ U/mL)* FPG (mg/dL)/405
- HOMA- β = 360 * Fasting insulin (μ U/mL)/ (FPG (mg/dL) – 63)

Efficacy variables units for analysis are described in Table 4.

Table 4 Efficacy Variable Units

Variables	Conventional Units	How to Convert	Units for Analysis
HbA1c	%	-	%
FPG	mg/dL	-	mg/dL
Fasting insulin	μ U/mL	-	μ U/mL
C-peptide	ng/mL	-	ng/mL
Glucagon	pmol/L	Multiply with 0.27241	pg/mL
HOMA-IR	-	-	-
HOMA- β	-	-	-
Body Weight	Kg	-	Kg

The efficacy variables will be evaluated for change from baseline. The change from baseline at post-baseline visits will be computed as:

- Change from baseline = Assessed/observed value at post-baseline visit – Value at baseline visit.

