8.7.3 Analysis of Other Efficacy Variables

All other efficacy endpoint will be analysed using FAS. The other efficacy endpoints are as follows:

- Proportion of subjects who achieved HbA1c < 7.0% at Week 24
- Change in fasting insulin, C-peptide, and glucagon from baseline to Week 24
- Change in HOMA-IR and HOMA- β from baseline to Week 24
- Change in body weight from baseline to Week 24
- Change in HbA1c and FPG from baseline to Week 12

Proportion of subjects who achieved HbA1c < 7.0% at Week 24 (LOCF):

For the proportion of subjects who achieved HbA1c < 7.0% at Week 24 (LOCF), the comparison between treatments will be performed using logistic regression with treatment as fixed effect and baseline HbA1c value as a covariate. The subjects who have HbA1c < 7.0% at baseline will be excluded from the analysis.

The odds ratio (OR) with 95% Wald CIs will be presented for between treatment groups comparison of responder rate (i.e. proportion of subjects who achieved HbA1c < 7.0% at Week 24). The Wald Chi-Square p-value for significance of treatment effect after controlling for baseline HbA1c will also be displayed.

For logistic regression analysis, the dichotomous response variable will be coded as '1' (for subjects who achieved HbA1c < 7.0% at Week 24) and '0' for subjects for whom HbA1c \geq 7.0% at week 24.

The frequency count and percentage of subjects who achieved HbA1c < 7.0% at week 24 will also be summarized by treatment groups.

Other efficacy endpoints:

For the remaining other efficacy endpoints, namely;

- Change in fasting insulin, C-peptide, and glucagon from baseline to Week 24
- Change in HOMA-IR and HOMA- β from baseline to Week 24

- Change in body weight from baseline to Week 24
- Change in HbA1c and FPG from baseline to Week 12

The line graph for mean change in other efficacy endpoints from baseline to Week 24 and Week 24 (LOCF) will be presented. The 95% CIs will also be shown in the graph with error bar. The plots of Week 24 and Week 24 (LOCF) will not be connected.

The same statistical methodology as described for primary analysis on primary efficacy endpoint will be used.

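### The glucagon conversion in SAP Table 4 (pmol/L times 0.27241 to give pg/mL) is dimensionally wrong and would put every glucagon result on the wrong scale

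*SAP*

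**What the plan says.** SAP section 6.7 gives Table 4 a binding role: "Efficacy variables units for analysis are described in Table 4". The glucagon row has pmol/L under *Conventional Units*, "Multiply with 0.27241" under *How to Convert*, and pg/mL under *Units for Analysis*. It is the only efficacy variable in the table with a conversion.

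On the source of the values, the same section says: "Blood sample will be analysed in designated central laboratory". The protocol's section on other efficacy parameters also sends glucagon to a central laboratory and names no unit.

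The converted values feed an efficacy endpoint listed in SAP 8.7.3: "Change in fasting insulin, C-peptide, and glucagon from baseline to Week 24". For the analysis, that section says: "The same statistical methodology as described for primary analysis on primary efficacy endpoint will be used". That means ANCOVA on Week 24 (LOCF) change with baseline as covariate, reporting LS means, the treatment difference, SE, CI and p-value. A graph is also specified: "The line graph for mean change in other efficacy endpoints from baseline to Week 24 and Week 24 (LOCF) will be presented". SAP 8.7 adds a full subject listing that includes glucagon.

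**The concern.** A molar concentration becomes a mass concentration through the molar mass. For a peptide hormone, which weighs thousands of g/mol, the number in pg/mL must be larger than the number in pmol/L. Multiplying by 0.27241 makes it smaller. At least one of the factor, the operation or the unit labels must therefore be wrong.

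At stake is the reported size of the glucagon effect. A programmer who follows the row would produce tables, a graph and possibly listings labelled pg/mL that are not in pg/mL. Multiplying every value by the same constant changes neither the p-value nor the direction of the effect, so the test result would look normal.

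**Working it through.** **Inputs.** The factor 0.27241 and the two units come from SAP Table 4. The documents give no molar mass for glucagon. I assume about 3,483 g/mol, from the composition C153H225N43O49S: 153 × 12.011 + 225 × 1.008 + 43 × 14.007 + 49 × 15.999 + 32.06 = 3,482.8. I show a range of 3,000 to 4,000.

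**Step 1: the plan's own figure.** 1 pmol/L = M pg/L = M/1000 pg/mL. Setting M/1000 = 0.27241 gives M = 272.4 g/mol. The factor is therefore not reproduced for any molecule near the assumed mass. That the row is wrong requires only M > 1,000 g/mol.

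**Step 2: is the table being read in the right direction?** SAP Table 5 (section 6.8.2) uses the same column headings, and its three conversions all work from conventional unit to analysis unit:
- Red cells, ×10^6/µL to ×10^4/µL: 10^6/10^4 = 100, printed as multiply by 10^2.
- White cells, ×10^3/µL to ×10/µL: 10^3/10 = 100, printed as multiply by 10^2.
- Platelets, ×10^3/µL to ×10^4/µL: 10^3/10^4 = 0.1, printed as divide by 10.

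The intended reading is left to right. This does not show that the two glucagon units were entered in the right cells.

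**Step 3: size of the error if the row is applied literally.**

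| Laboratory reports | Formula | M = 3,000 | M = 3,483 | M = 4,000 |
|---|---|---|---|---|
| pmol/L | (M/1000)/0.27241 | 11.0-fold too small | 12.8-fold too small | 14.7-fold too small |
| pg/mL | 1/0.27241 | 3.67-fold too small | 3.67-fold too small | 3.67-fold too small |

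As an illustration, with a value chosen for this purpose: 20 pmol/L becomes 20 × 0.27241 = 5.4 labelled pg/mL, when the true value is 20 × 3.483 = 69.7 pg/mL (60 to 80 over the range).

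**Step 4: would a simple repair make the row exact?**
- *Swap the unit labels* (pg/mL in, pmol/L out). The correct factor is 1000/M = 0.2871 at M = 3,483. The printed factor gives 0.27241 × 3.483 = 0.949, so 5.1% too low (18.3% too low at 3,000; 9.0% too high at 4,000).
- *Change multiply to divide.* 1/0.27241 = 3.671, and 3.671/3.483 = 1.054, so 5.4% too high (22.4% too high at 3,000; 8.2% too low at 4,000).

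Either repair is exact only at M = 1000/0.27241 = 3,671 g/mol. These percentages are what would remain after a repair, not the error in the row as printed.

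**Step 5: effect on the analysis.** In the ANCOVA, multiplying both the change and the baseline by a constant c multiplies the treatment estimate and its SE by c, so their ratio t and the p-value stay the same. A simulated data set (120 per group, arbitrary values) confirmed this:

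| c | Estimate | SE | p |
|---|---|---|---|
| 1 | −0.227 | 0.577 | 0.6939 |
| 0.27241 | −0.062 | 0.157 | 0.6939 |
| 3.483 | −0.792 | 2.011 | 0.6939 |

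The HOMA-IR and HOMA-β formulas in SAP 6.7 use only insulin and FPG, so the error does not reach them.

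**The case against.** The strongest case on the other side is about weight, since the row itself cannot be defended.

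- **Reach.** Glucagon change is one of several endpoints below primary and secondary. No eligibility rule, discontinuation rule, subgroup or safety endpoint depends on it, and its own significance test is unaffected. This stands, and it limits the importance of the point.
- **Other safeguards.** SAP 7.1 and 8.7 plan listings of collected and derived data, and SAP 9 applies quality-control procedures to all displays. A 12.8-fold shift might be noticed there. That is possible but not assured: the listings may show only converted values, and a check against the SAP would find the program following its specification.
- **Shells not seen.** The SAP contents list table and listing shells (sections 12 and 13) that were not in the text reviewed and could show a glucagon unit. The statement that nothing corrects the row is limited to the text reviewed. A different unit in a shell would add a second version without removing the conflict inside Table 4.
- **Outside input.** The molar mass is an assumption. The 12.8-fold figure depends on it, and also on the laboratory reporting pmol/L. The 3.67-fold figure and the conclusion that the row is wrong do not depend on the exact mass.

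**Conclusion.** The concern holds. The three glucagon entries in Table 4 cannot all be right for a molecule heavier than 1,000 g/mol. If the row is followed, glucagon results labelled pg/mL are too small by 12.8-fold (11.0 to 14.7 for molar masses of 3,000 to 4,000 g/mol) when the laboratory reports pmol/L, or by 3.67-fold when it reports pg/mL. The documents do not show which entry is wrong. Because neither simple repair is exact at 3,483 g/mol, the factor needs checking along with the labels.

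Confidence is high that the row is wrong and moderate on the size, which depends on the laboratory's unit. The p-value is protected only if all results arrive in one unit; nothing in the documents suggests otherwise. The error should be corrected, but it does not touch the trial's main conclusions.

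**What to change.** Before database lock, obtain the central laboratory's reporting unit for glucagon in writing, then make all three cells of the row agree:

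- **Laboratory reports pmol/L:** either analyse in pmol/L with no conversion, or convert to pg/mL with M/1000 (about 3.48 under the assumption here, to be confirmed with the laboratory).
- **Laboratory reports pg/mL:** analyse in pg/mL with no conversion. If pmol/L was the intended analysis unit, use a confirmed 1000/M (about 0.287 under the same assumption) and label the output pmol/L.

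Check that the table, graph and listing shells show the same unit. The cost is one row of SAP Table 4 and one line of derivation code, with no new data.

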6.8 Safety Assessments

6.8.1 Adverse Events

All adverse events (AEs) or hypoglycaemia episodes occurring after signing the informed consent are to be recorded on the AE or the hypoglycaemia episode pages of the CRF. Investigators verbatim term of AE and hypoglycaemia episode will be mapped to system organ class (SOC) and preferred term (PT) using MedDRA version 21.0. All hypoglycaemia episodes will be coded as “Hypoglycaemia” (LLT code=10020993, ver21.0).

Duration of adverse events will be derived as:

- Duration of AE (Days) = End Date - Start Date +1

6.8.1.1 Definitions

Treatment Emergent Adverse Events (TEAEs):

TEAEs are defined as any AEs or hypoglycaemia episodes that occur or worsen (increase in severity) on the same day or after randomized.

The following rules will apply in cases where the start date of an AE is known:

- If the AE onset date is prior to Day 1, then the AE will not be considered a TEAE.
- If the AE onset date or date of AE worsening is equal to or later than Day 1, then the AE will be considered a TEAE.

The same rule will be applied in cases where start date of a hypoglycemic episode is known.

Refer section 7.3.1 to identify TEAE status when start date of an AE or hypoglycaemia episodes is unknown.

Adverse Drug Reactions (ADRs):

ADRs are defined as TEAE whose causal relationship to study drug is “Reasonable possibility”. If the causal relationship to study drug is missing, then that TEAE will be treated as ADR.

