6.3.3 Withdrawals and Replacement of Subjects

Subjects may be discontinued from study at any time. Subjects are also free to discontinue their participation in the study at any time without prejudice to further treatment.

In the eCRF, study completion or discontinuation will be documented with the reason for any discontinuation. Possible reasons for a subject discontinuing participation in the study are:

- AE(s) that endanger the health of subjects, making it ethically unacceptable to continue
- Deterioration of the subject's clinical condition(s) that requires appropriate therapy/treatment during the study period
- Withdrawal of consent
- Other cases where the investigator decides the study for the relevant subject should be discontinued.

Subjects' condition are clearly no longer suitable to continue in the study. The subjects with a lack of glycaemic control during the double-blind treatment period will be discontinued from the study and referred to appropriate anti-hyperglycaemic therapy. Inadequate FPG measured in the central laboratory is defined as follows:

- (1) FPG > 270 mg/dL (15 mmol/L) from baseline to Week 8 (inclusive).
- (2) FPG > 240 mg/dL (13.3 mmol/L) from Week 8 to Week 12 (inclusive).
- (3) FPG > 200 mg/dL (11.1 mmol/L) from Week 12 to Week 24 (exclusive).

In case of an AE, the subject should be followed up, whenever possible, until the subject recovers or until the investigator considers the situation to be no longer clinically significant. Subjects who discontinue prematurely from the study will not be replaced.

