6.5 Prior and Concomitant Therapy

6.5.1 Prohibited Concomitant Medications

(1) Anti-diabetic drugs

Concomitant use of the following medications is not permitted within at least 8 weeks before the screening visit until 2 weeks after the final dose of the study drug. Subjects may use the following medications after 2 weeks after the final dose of the study drug including the early termination if required when judged by the investigator: Insulin, sulfonylureas, alpha-glucosidase inhibitors, thiazolidinediones, Repaglinide, DPP-4 inhibitors, GLP-1 receptor agonists, herbal medicines that lower blood glucose levels, new drugs intended for diabetes, fixed dose combination tablets including above active ingredients.

Subjects can use the anti-diabetic treatment after Early termination visit when the subject discontinue the study due to a lack of glycaemic control.

(2) Others

The following medications are not permitted in the period from the screening visit to 2 weeks after the final dose of the study drug out of a concern for the influence on the efficacy and safety assessment. Subjects may use the following medications after 2 weeks after the final dose of the study drug including the early termination if required when judged by the investigator: Adrenocorticosteroids (excluding for external use) for more than 2 consecutive weeks and other investigational products (including placebo)

Subjects can use the adrenocorticosteroids after Early termination visit when the investigator consider that the treatment is necessary.

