6.5.3 Treatment with Metformin

Treatment with metformin (≥ 1000 mg/day) will be continued without any changes to the dosage and/or the dose regimen from at least 8 weeks before the screening visit to the final dose of the study drug. The metformin prescribed in the sites will continue to be prescribed and dispensed during the study.

Subjects may change the dosage and/or the dose regimen after the final dose of the study drug including the early termination if required when judged by the investigator.

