- Subjects are to be instructed that they have to return for the next scheduled visit day.

Treatment Visit 5 (Week 20 plus/minus 7 days of treatment)

The following observations/procedures are to be performed and checked:

- Vital signs, body weight
- Review use of concomitant treatments and of the regular metformin therapy
- Blood and urine is to be drawn and sent to the central laboratory according to the local procedure for evaluation of haematology, clinical chemistry, urinalysis, HbA1c, FPG, fasting insulin, C-peptide and glucagon
- Evaluation for any AEs including hypoglycaemic episodes experienced by the subjects since last visit
- Review subject diary
- MP-513 or placebo will be dispensed to the subjects. Unused medication has to be returned to the site
- Subjects are to be instructed that they have to return for the next scheduled visit day.

Treatment Visit 6 (Week 24plus/minus 7 days of treatment /Early termination visit: date of discontinuation* plus 7 days)

*Date of discontinuation is defined as the date of decision of discontinuation for subjects by the investigator.

This visit is the regular **end of treatment visit**. In case of premature termination, the same evaluations have to be performed as **the early termination visit**.

The following observations/procedures are to be performed and checked:

- Vital signs, body weight and ECG
- Review use of concomitant treatments and of the regular metformin therapy
- Blood and urine is to be drawn and sent to the central laboratory according to the local procedure for evaluation of haematology, clinical chemistry, urinalysis and HbA1c, FPG, fasting insulin, C-peptide and glucagon.
- A serum pregnancy test is to be performed in females with childbearing potential.
- Evaluation for any AEs including hypoglycaemic episodes experienced by the subjects since last visit
- Review and final collection of subject diary
- Unused MP-513 or placebo has to be returned to the site.

Follow-up Visit (Week 26 plus 14 days following completion / Early termination of double-blind treatment period)

Two weeks after end of treatment, a telephone follow-up visit will take place to ask the subjects about any AEs including hypoglycaemic episodes experienced by the subjects since the last visit and use of concomitant treatments.

- Review of the use of the regular metformin therapy.

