6 BASELINE, EFFICACY AND SAFETY EVALUATIONS

6.1 Schedule of Evaluations

The assessments to be conducted at each scheduled visit are displayed in the below table.

Table 2 Schedule of Visits

Period	Scr. Period	Placebo Run-in Period	Double-Blind Treatment Period						Follow-up Period	
Visit	SV	PV	RV	V1	V2	V3	V4	V5	V6	FV
Visiting Windows	Day -28 +/- 3 days	Day -14 +/- 3 days	Day 1	Week 4 +/- 7 days	Week 8 +/- 7 days	Week 12 +/- 7 days	Week 16 +/- 7 days	Week 20 +/- 7 days	Week 24 ⁽⁵⁾ +/- 7 days	Week 26 ⁽⁶⁾ + 14 days
Items										
Obtain written informed consent	X									
Screening/Inclusion/Exclusion criteria evaluation	X	X	X							
Demographics and complete medical history	X ⁽⁷⁾									
Height	X									
Body Weight	X		X	X	X	X	X	X	X	
Vital signs ⁽¹⁾	X	X	X	X	X	X	X	X	X	
12-lead ECG	X		X			X				X
Routine laboratory evaluations: hematology, chemistry, urinalysis	X		X	X	X	X	X	X	X	
Serum pregnancy test ⁽²⁾	X									X
HbA1c	X	X	X	X	X	X	X	X	X	
Fasting plasma glucose	X	X	X	X	X	X	X	X	X	
Fasting insulin, C-peptide and glucagon			X	X	X	X	X	X	X	
Dispense medication			X	X	X	X	X	X	X	
Return of unused medication				X	X	X	X	X	X	X
Assessment of adverse events ⁽³⁾ and concomitant medication	X	X	X	X	X	X	X	X	X	X
Hypoglycaemic episodes ⁽⁴⁾	X	X	X	X	X	X	X	X	X	X
Dispense subjects diary and glucometer	X									
Subject diary review		X	X	X	X	X	X	X	X	

Scr period: Screening period, SV: Screening visit, PV: Placebo run-in visit, RV: Randomization visit, FV: follow-up visit

(1) Vital signs (sitting blood pressure, pulse rate and body temperature)

(2) The serum pregnancy test will be performed only for female subjects of childbearing potential.

(3) AEs will be collected and reported on the eCRF from the date of informed consent to 14 days after the final dose of the study drug considering the half-life (T1/2) of MP-513.

(4) The occurrence of hypoglycaemic episodes will be recorded continuously throughout the study by a subject diary

(5) These assessments will also be performed at early termination.

(6) Telephone visit

(7) Including physical examination

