8.8.1 Adverse Events

All AE summary tables will include only TEAEs, unless otherwise specified.

Adverse events will be summarized by SOC and PT. A subject will only be counted once per SOC and PT within a treatment.

For AEs by severity grade (mild, moderate, severe), if a subject has multiple events occurring in the same SOC or same PT, then the event with the maximum intensity (i.e. severe) will be counted.

For AEs by relationship to study drug, if a subject has multiple events occurring in the same SOC or same PT, the event with the highest association (i.e. related) to study drug will be summarized.

Adverse events will be presented in Internationally Agreed Order at SOC level and within each SOC, in decreasing order of the incidences (in MP-513, then in Placebo) at the PT level.

An overall summary of adverse events will be presented and will include:

- Subjects with at least one TEAE
- Subjects with any severe TEAE
- Subjects with any serious TEAE
- Subjects with any ADRs

- Subjects with any serious ADRs
- Subjects with any treatment emergent cardiovascular events
- Subjects with any study drug related treatment emergent cardiovascular events
- Subjects with any TEAE resulting in death
- Subjects with any ADR resulting in death
- Subjects with any TEAE leading to drug discontinuation
- Subjects with any ADR leading to drug discontinuation
- Subjects with Hypoglycaemia
- Subjects with study drug related Hypoglycaemia

The following summary tables will be presented by SOC and PT:

- All TEAEs
- TEAEs by relationship to study drug
- TEAEs by severity grade
- Serious TEAEs
- Treatment emergent cardiovascular events
- Study drug related treatment emergent cardiovascular events
- All ADRs
- Serious ADRs
- TEAEs leading to drug discontinuation,
- ADRs leading to drug discontinuation

The following listings will be presented by subject:

- All AEs
- TEAEs
- Serious TEAEs
- TEAEs leading to drug discontinuation
- Treatment emergent cardiovascular events
- All ADRs
- All hypoglycaemic episodes

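### The all-cause hypoglycaemia count has no stated end and no cut when a withdrawn subject starts another glucose-lowering drug (minor; descriptive safety only)

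*SAP*

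**What the plan says.** **Counting rule.** SAP 6.8.1.1 defines the events as follows: "TEAEs are defined as any AEs or hypoglycaemia episodes that occur or worsen (increase in severity) on the same day or after randomized". For known dates the operating rule asks only whether onset or worsening falls on or after Day 1. The rules for unknown dates in SAP 7.3.1 also refer only to Day 1. SAP 8.8.1 builds its AE summary tables on TEAEs and includes a row headed "Subjects with Hypoglycaemia", with a second row for hypoglycaemia judged related to study drug.

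**New drugs after withdrawal.** Under Protocol 6.3.3, subjects who exceed the FPG limits "will be discontinued from the study and referred to appropriate anti-hyperglycaemic therapy". Protocol 6.5.1 generally bars the listed anti-diabetic drugs, among them insulin, sulfonylureas and repaglinide, until two weeks after the final dose. It then makes an exception: "Subjects can use the anti-diabetic treatment after Early termination visit when the subject discontinue the study due to a lack of glycaemic control".

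**Collection.** SAP 6.1 (footnote 3) says AEs are "collected and reported on the eCRF from the date of informed consent to 14 days after the final dose of the study drug". Footnote 4 describes hypoglycaemia recording as running for the whole study through the diary and gives no 14-day limit. Protocol 6.6.2.4 has the diary checked up to the last dose, and Protocol 6.6.1 has it collected for the last time at Week 24 or early termination. The telephone follow-up two weeks after the end of treatment is still to "ask the subjects about any AEs including hypoglycaemic episodes experienced by the subjects since the last visit and use of concomitant treatments".

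**The concern.** The two weeks after the final dose are otherwise kept free of other anti-diabetic drugs. The exception opens that period for one group only: subjects whose glucose was too high. Treatment is meant to change that very outcome, so membership of the group may differ by arm. An episode on newly started insulin or a sulfonylurea would then count as a treatment-emergent episode of the arm in which the subject is analysed.

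Hypoglycaemia is a named safety endpoint (Protocol 6.9.1.6), and the rationale in Protocol section 4 presents MP-513 as free of hypoglycaemia risk. If more placebo subjects are withdrawn for poor control, their later episodes raise the placebo count and make MP-513 look relatively better. When few events are expected, one or two subjects can visibly change the row.

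**Working it through.** The documents give no hypoglycaemia incidence and no rate of withdrawal for poor control by arm. The 30% drop-out in SAP 4.5 is not split by arm or by reason. There is therefore no stated figure to reproduce on this point. The check is a comparison of sections, followed by an illustration on assumed inputs.

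**Step 1: is there an end or a cut?** SAP 6.8.1, 6.8.1.1, 7.3.1 and 8.8.1 contain no upper date and no rule tied to another drug. The definition is open-ended. Data collection is not.

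**Step 2: how long is the exposed window?**
- Under the AE limit, collection stops 14 days after the final dose. The early termination visit may fall up to 7 days after the decision to discontinue. Taking the last dose to fall between that decision and the visit (an assumption), the window after the visit is 14 − 7 = 7 days up to 14 days. For scale, 14/182 = 7.7% of Days 1 to 182.
- If the whole-study wording governs hypoglycaemia, the window can run to the end of the follow-up window (SAP 6.2.2): 196 − 168 = 28 days, or 28/196 = 14.3%.

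**Step 3: who is exposed?** Only subjects withdrawn for lack of glycaemic control. Completers, and subjects withdrawn for other reasons, remain under the two-week bar.

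**Step 4: size.** From the SAP: n = 120 per arm. Assumed: proportion withdrawn for poor control of 5–15% on placebo (w_P) and 2–3% on MP-513 (w_M), and a 5–15% chance (q) that such a subject has an episode on the new drug while still followed.

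Extra subjects per arm = 120 × w × q. Shift in percentage points = 100 × (w_P − w_M) × q.

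| Case | w_P | w_M | q | Extra placebo | Extra MP-513 | Shift (points) |
|---|---|---|---|---|---|---|
| Low | 5% | 3% | 5% | 0.30 | 0.18 | 0.10 |
| Central | 10% | 3% | 10% | 1.20 | 0.36 | 0.70 |
| High | 15% | 2% | 15% | 2.70 | 0.36 | 1.95 |
| Equal withdrawal | any | same | any | same | same | 0 |

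If 2% of each arm (2.4 subjects) also have an on-treatment episode, again an assumption, and these are different people, the central case reports (2.4 + 1.2)/120 = 3.0% on placebo against (2.4 + 0.36)/120 = 2.3% on MP-513, where the on-treatment rates are equal.

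A second set of assumptions (5% vs 2% up to 20% vs 6% withdrawn, q from 2% to 10%) gives (0.05 − 0.02) × 0.02 = 0.06 points to (0.20 − 0.06) × 0.10 = 1.4 points.

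**The case against.** The case for leaving the plan alone is reasonable, and several parts of it stand.

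- **Collection is bounded.** A reader might infer from the definition that episodes are counted indefinitely. They are not: AE collection ends 14 days after the final dose, and the follow-up call is the last contact. The exposure lasts one to four weeks and is picked up mainly by recall on the telephone. This stands.
- **The plan partly separates the episodes.** Causality is recorded for each episode, there is a drug-related row, and hypoglycaemic episodes and concomitant medications are both listed by subject (SAP 8.5, 8.8.1), so a case can be traced by hand. This stands in part. The drug-related row is a coarse filter: Protocol 6.6.2.4 places possibly-not-related and unassessable events on the related side, and SAP 6.8.1.2 treats missing causality as related. The all-cause row has no filter.
- **A placebo-directed bias is not shown.** A reader might infer that these episodes fall mostly on placebo. That follows if MP-513 lowers glucose, but no figure in the documents supports it, and with equal withdrawal the shift is zero. The high case also needs every input at the edge of its range.
- **Metformin adds nothing.** Protocol 6.5.3 says "Subjects may change the dosage and/or the dose regimen after the final dose of the study drug including the early termination", and a reader might count this as a further source. The documents themselves describe metformin as not causing hypoglycaemia (Protocol section 4, SAP 4.2), and the permission covers completers in both arms.
- **The arm is not strictly the randomised one.** SAP 8.3 analyses anyone who ever received MP-513 as MP-513. This matters only for misallocated subjects.
- **Counting all collected events is a legitimate convention.** It is, and cutting at the new drug shortens observation for withdrawn subjects. That argues for keeping the all-episode row and adding a second one, not for replacing it.

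**Conclusion.** The point holds as a minor one. The counting rule has no stated end, and in the all-cause row and the TEAE tables it mixes in episodes that occur after a withdrawn subject has started another anti-diabetic drug. The subjects concerned are selected by an outcome that treatment may affect.

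On the assumed inputs the comparison moves by about 0.1 to 2 percentage points towards MP-513. The central case is 1.2 − 0.36 = 0.84 of a subject in 120. The direction depends on poor-control withdrawal being commoner on placebo, and the size rests wholly on assumed withdrawal and episode rates. No safety test is planned (SAP 8.8), so no decision rule is affected. The documents do not support a claim of unlimited counting or of a demonstrated bias.

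**What to change.** In SAP 6.8.1.1 and 8.8.1:

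1. State that the TEAE period, including hypoglycaemia, ends 14 days after the final dose, matching AE collection. Reconcile this with the footnote that has hypoglycaemia recorded for the whole study, and with the diary check that stops at the last dose.
2. Keep the all-episode hypoglycaemia row.
3. Add a row for subjects with hypoglycaemia up to first use of any anti-diabetic drug other than study drug and background metformin. Flag later episodes in the hypoglycaemia listing.

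The cost is one derived flag. Episode dates and concomitant drug use are already collected, the latter up to the follow-up call. The drawback is slightly shorter observation for withdrawn subjects in the added row, which a table footnote should state. No event is dropped from the report and no treatment rule changes.
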